4.2.1.6 Supplementary Analyses of the key objective

Not applicable.

4.2.1.7 Subgroup Analyses

The primary analysis of this endpoint will be performed for the subgroups defined in section 3.3.1.7 if appropriate.

4.2.2 Key Objective 3 and 4, Change from baseline in body weight (based on values obtained both at home, and at the site), water volumes and body fat mass

4.2.2.1 Definition

Estimand is defined in section 4.2.

4.2.2.2 Derivations

Home body weight which is measured daily will be represented weekly by taking the average of the daily measurement each week and use that for the analyses.

4.2.2.3 Handling of Dropouts and Missing Data

Missing data is assumed to be MAR and no imputation will be done.

4.2.2.4 Primary Analysis of key objective

Will be analysed using MMRM methodology. The analytic model will include CCI [REDACTED] CCI [REDACTED] of CCI [REDACTED] and CCI [REDACTED] and CCI [REDACTED] CCI [REDACTED] will be used for CCI [REDACTED]. An CCI [REDACTED] will be used for CCI [REDACTED].

4.2.2.5 Sensitivity Analyses of the key objective

Following analysis for evaluating impact of analyses method and missing data will be done:

- To analyse the method choice of MMRM the analyses will be performed using ANCOVA after missing data has been imputed under MAR assumption using multiple imputation. A total of 1000 imputations will be performed using a seed of 4567.

4.2.2.6 Supplementary Analyses of the key objective

Not applicable.

4.2.2.7 Subgroup Analyses

The primary analysis of this endpoint will be performed for the subgroups defined in section 3.3.1.7 if appropriate.

4.2.3 Key Objective 5 and 6, Change from baseline in Loop-diuretic usage

4.2.3.1 Definition

Estimand is defined in section 4.2.

4.2.3.2 Derivations

See section 3.3.1.5.

4.2.3.3 Handling of Dropouts and Missing Data

For missing partial dates for loop-diuretics see section 3.3.1.4. Other missing data is assumed to be MAR and no imputation will be done.

4.2.3.4 Primary Analysis of key objective

Will be analysed using MMRM methodology. The analytic model will include CCI [REDACTED] CCI [REDACTED] of CCI [REDACTED], and CCI [REDACTED], and CCI [REDACTED]. CCI [REDACTED] CCI [REDACTED]. An CCI [REDACTED] will be used for CCI [REDACTED].

4.2.3.5 Sensitivity Analyses of the key objective

Following analysis for evaluating impact of analyses method and missing data will be done:

- To analyse the method choice of MMRM the analyses will be performed using ANCOVA.

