3.3.1.5 Loop diuretic equivalents

Table 2 Loop-diuretic equivalents

Drug	Global dose equivalent ^a	Japan dose equivalent
Furosemide	40	40
Bumetanide	1	N/A
Torsemide	20	8
Azosemide	N/A	60
Etacrynic/Ethacrynic acid	50	N/A

^a Will be used for all countries except Japan.

For analyses of loop-diuretic equivalents, the cumulative actual loop equivalents taken will be compared to the what the participant would have taken if continued to take equivalents as he/she did at baseline.

3.3.1.6 eGFR, MELD score and Child-Pugh score calculations

eGFR

The participant's eGFR will be calculated based on two different equations. eGFR1 is according to the 2021 CKD-EPI equation, based on serum creatinine concentration alone (Inker et al, 2021). eGFR2 will be calculated based on both serum creatinine and serum cystatin C concentrations (Inker et al, 2021).

$$\text{eGFR1} = 142 \times \min(S_{\text{cr}}/\kappa, 1)^{-0.241 \text{ (if female)} / -0.302 \text{ (if male)}} \times \max(S_{\text{cr}}/\kappa, 1)^{-1.200} \times 0.9938^{\text{Age}} \times 1.012 \text{ [if female]}$$

$$\text{eGFR2} = 135 \times \min(S_{\text{cr}}/\kappa, 1)^{-0.219 \text{ (if female)} / -0.144 \text{ (if male)}} \times \max(S_{\text{cr}}/\kappa, 1)^{-0.544} \times \min(S_{\text{cys}}/0.8, 1)^{-0.323} \times \max(S_{\text{cys}}/0.8, 1)^{-0.778} \times 0.996^{\text{Age}} \times 0.963 \text{ [if female]}$$

Where:

S_{cr} = serum creatinine (mg/dL)

S_{cys} = serum cystatin C (mg/L)

κ = 0.7 for females; and 0.9 for males

min = minimum of S_{cr}/κ or 1

max = maximum of S_{cr}/κ or 1

MELD score

The Model for end stage liver disease score, MELD score, is calculated for each visit according to:

$$\text{MELD} = 3.78 \times \ln[\text{serum bilirubin (mg/dL)}] + 11.2 \times \ln[\text{INR}] + 9.57 \times \ln[\text{serum creatinine (mg/dL)}] + 6.43$$
 If bilirubin, INR and/or creatinine values are less than 1.0, the value is set as 1.0.

Child-Pugh score

Child-Pugh score is calculated according to table [Table 3](#).

Table 3 Child-Pugh Score

Clinical and laboratory criteria	Points		
	1	2	3
Encephalopathy	None	Mild to moderate (West Haven grade 1 or 2)	Severe (West Haven grade 3 or 4)
Ascites	None	Mild to moderate (diuretic responsive)	Severe (diuretic refractory)
Bilirubin (mg/dL)	< 2	2 - 3	> 3
Albumin (g/dL)	> 3.5	2.8 – 3.5	< 2.8
Prothrombin time Seconds prolonged INR	< 4 < 1.7	4 - 6 1.7 – 2.3	> 6 > 2.3
Child-Turcotte-Pugh class obtained by adding score for each parameter (total points)			

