Primary analysis	
Occurrence of any of the following components of this composite endpoint from baseline to Week 6:
 
 • > 2 kg increase from baseline in body weight (office-based) • > 2 L increase from baseline in total body water • Increase from baseline in 2 or more loop-diuretic equivalents^a • Fluid retention AEs 	
Estimand population: See above for respective arms.
 
Analysis set: FAS
	Treatment policy strategy	Risk difference	4.2.1
Key objective 3: To evaluate the effect of zibotentan/dapagliflozin versus corresponding zibotentan monotherapy on body weight, body water volumes, and body fat mass.					
Primary analysis	
Change in body weight (kg) over time course of study (home-based monitoring).
 
Change from baseline in body weight, total body water, extracellular and intracellular water volumes, body fat mass at Week 6 (office-based monitoring).
	
Estimand population: See above for respective arms.
 
Analysis set: FAS
	Treatment policy strategy	Least square mean difference in change from baseline	4.2.2
Key objective 4: To evaluate the effect of zibotentan/dapagliflozin and zibotentan monotherapy versus placebo on body weight, body water volumes, and body fat mass.					

Statistical / Estimand category	Endpoint	Population/Analysis set	Intercurrent event strategy	Population level summary (analysis)	Details in section
Primary analysis	
Change in body weight (kg) over time course of study (home-based monitoring).
 
Change from baseline in body weight, total body water, extracellular and intracellular water volumes, body fat mass at Week 6 (office-based monitoring).
	
Estimand population: See above for respective arms.
 
Analysis set: FAS
	Treatment policy strategy	Least square mean difference in change from baseline	4.2.2
Key objective 5: To evaluate the effect of zibotentan/dapagliflozin versus corresponding zibotentan monotherapy on total loop-diuretic equivalents use. ^a					
Primary analysis	Change in total dosage of loop-diuretic equivalents use from baseline to Week 6 ^a .	
Estimand population: See above for respective arms.
 
Analysis set: FAS
	Treatment policy strategy	Least square mean difference in change from baseline	4.2.3
Key objective 6: To evaluate the effect of zibotentan/dapagliflozin and zibotentan monotherapy versus placebo on total loop-diuretic equivalents use. ^a					

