4.2.1.5 Sensitivity Analyses of the key objective

Following analysis for evaluating impact of missing data will be done:

- A conservative imputation approach will be conducted and missing data will be imputed for each component separately except for component of fluid retention AEs and loop-diuretics. For the placebo group, missing data will be imputed as “No event”. For the zibotentan/dapagliflozin and zibotentan monotherapy treatment

groups the missing data will be imputed based on the overall probability for “Event” at a given visit in the combined zibotentan/dapagliflozin and zibotentan monotherapy treatment groups. This probability will be estimated using the observed probability. Seed 3456 will be used. For component of fluid retention AEs, no imputation will be done. For component of loop-diuretics, having no reported loop-diuretics is not considered as missing data. The analyses method will follow section 4.2.1.4.

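### The loop-diuretic sensitivity analysis (SAP 4.2.3.5) is said to assess missing data but specifies an ANCOVA with no imputation step, unlike its two sister sections

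*SAP*

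**What the plan says.** - **Endpoint.** Key objectives 5 and 6 concern "Change in total dosage of loop-diuretic equivalents use from baseline to Week 6" (SAP 4.2, Table 7). Under SAP 3.3.1.5 the variable is cumulative: "the cumulative actual loop equivalents taken will be compared to the what the participant would have taken if continued" at the baseline rate. SAP 3.3.2, Table 6, windows it weekly, with Week 6 as Days 37 to 43.
- **Primary analysis.** An MMRM (SAP 4.2.3.4). On missing data, 4.2.3.3 refers partial dates to a date rule and adds: "Other missing data is assumed to be MAR and no imputation will be done".
- **Sensitivity analysis.** SAP 4.2.3.5 opens with "Following analysis for evaluating impact of analyses method and missing data will be done". Its only bullet is "To analyse the method choice of MMRM the analyses will be performed using ANCOVA". It gives no imputation, time point, covariates or rule for people who leave. SAP 4.2.3.6 lists no supplementary analysis.
- **Sister sections.** SAP 4.2.2.5 (weight, water, fat) and 4.2.5.5 (blood pressure) share the opening line but specify "ANCOVA after missing data has been imputed under MAR assumption using multiple imputation", and then "A total of 1000 imputations will be performed using a seed of 4567".

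**The concern.** The SAP promises a missing-data check for a key safety endpoint and does not describe one. An ANCOVA uses one outcome per participant. Without imputation, anyone lacking that outcome would ordinarily be left out. The MMRM keeps such a person's earlier weekly values, so the check would use less information than the analysis it is meant to test and would rest on a stronger missingness assumption.

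Two things follow. First, if the ANCOVA and the MMRM disagree, both the method and the set of participants have changed, and the cause cannot be identified. Second, participants who need more diuretic may be the ones who leave. In that case the ANCOVA contrast could move toward no difference through selection alone.

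**Working it through.** The documents state no figure for this endpoint that could be reproduced: the inputs to the precision statement in protocol 9.2 are redacted. The check is therefore a comparison of sections, followed by simulations with assumed inputs.

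**1. The three sections side by side**

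| SAP section | Stated purpose | Primary missing-data rule | Sensitivity analysis |
|---|---|---|---|
| 4.2.2.5 weight, water, fat | method and missing data | MAR, no imputation | ANCOVA after multiple imputation, 1000 imputations, seed 4567 |
| 4.2.3.5 loop diuretics | method and missing data | MAR, no imputation | ANCOVA |
| 4.2.5.5 blood pressure | method and missing data | MAR, no imputation | ANCOVA after multiple imputation, 1000 imputations, seed 4567 |

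The no-imputation rule is common to all three, so it describes the primary analysis and does not explain the difference. Only the loop-diuretic section lacks an imputation step, and no reason is given.

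**2. Who could lack a Week 6 value.** Protocol 7.1 keeps participants who stop study drug in the study. The value is at risk only for those who withdraw from the study, are lost to follow-up or die before Day 37. Someone leaving in Week 5 (Days 30 to 36) already has four complete weekly values, which the MMRM can use.

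**3. Precision.** With 22 per arm (protocol 9.2) and m lost from each arm, the CI widens by √(22/(22 − m)): 1.024 for m = 1, 1.049 for m = 2, 1.076 for m = 3, 1.106 for m = 4.

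**4. Bias, assumed inputs.** Two arms of 22; Normal outcomes with SD 1 at Weeks 3 and 6; half the Week 6 effect present at Week 3; 2,000 runs per row. Participants with the highest Week 3 values leave. Imputation is a single regression on Week 3, a simple stand-in for multiple imputation under MAR. Shrinkage = 1 − (observed-case ÷ full-data).

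| Assumed effect (SD) | Overall dropout | Lost, control / zibotentan | Full data | Observed-case ANCOVA | After imputation | Shrinkage |
|---|---|---|---|---|---|---|
| 0.5 | 5% | 3.3% / 5.8% | 0.496 | 0.468 | 0.496 | 5.6% |
| 0.5 | 10% | 6.8% / 11.3% | 0.509 | 0.462 | 0.509 | 9.2% |
| 0.5 | 20% | 16.8% / 24.1% | 0.507 | 0.439 | 0.507 | 13.4% |
| 1.0 | 5% | 2.4% / 6.7% | 0.984 | 0.934 | 0.984 | 5.1% |
| 1.0 | 10% | 5.3% / 12.9% | 1.001 | 0.925 | 1.001 | 7.6% |
| 1.0 | 20% | 13.6% / 27.3% | 0.991 | 0.868 | 0.995 | 12.4% |

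With random dropout and an effect of 1.0, the observed-case ANCOVA gives 1.012, 0.993 and 1.003 against full-data 1.011, 0.995 and 1.001, so there is no bias. With no true effect it stays near zero.

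**5. A harsher assumption.** A second simulation used cumulative use directly: added diuretic in 35% (zibotentan) against 10% (placebo), and a weekly leaving hazard of 5%, 8% or 12% once excess use was observed, otherwise 1%; 2,500 trials each. Full-data differences were 7.09, 6.99 and 7.17 equivalents. Completers gave 6.45, 5.86 and 5.38, which is 9%, 16% and 25% lower. Multiple imputation from earlier weeks gave 6.99, 7.01 and 7.10.

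For scale, take 7.1 equivalents with equal excess per user: 7.1 ÷ (0.35 − 0.10) = 28.4 per user. The SE is √[(0.35 × 0.65 + 0.10 × 0.90) × 28.4² ÷ 22] ≈ 3.4, and the 90% half-width is about 1.68 × 3.4 = 5.7. The shifts of 0.64 to 1.79 are about 0.2 to 0.5 SE.

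**6. The alternative of counting zero use.** Suppose a participant uses one equivalent a day at baseline and leaves after Day 29. If Days 30 to 43 counted as no use, the SAP 3.3.1.5 comparison would show a decrease of 14 × 1 = 14 equivalents that nobody observed.

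**The case against.** **Omitting imputation may be deliberate.** Loop-diuretic use comes from medication records, not visit measurements. Partial dates are filled by rule (SAP 3.3.1.4), and for the fluid-retention composite the SAP says that "having no reported loop-diuretics is not considered as missing data" (4.2.1.5). This stands as a reason to expect little missing data while a participant is on study. It does not close the gap. The sentence sits in the composite section, is not carried into 4.2.3, and does not say what value follows study withdrawal. SAP 4.2.3.3 itself provides for other missing data.

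**Few are affected and nothing decisive depends on it.** This stands. Participants who stop study drug are followed, and those who withdraw have an Early Termination Visit where possible (protocol 7.2). The MMRM keeps partial data, and the composites retain any event that occurred before leaving (SAP 4.2.1.2, 4.2.4.2). No hypothesis is tested (SAP 3.3.4).

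**Multiple imputation under MAR repeats the MMRM's assumption.** This also stands. It separates method from participant set but does not probe departures from MAR.

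**Stronger readings that the documents do not support.** A reader might infer that the SAP prescribes a completers-only analysis that drops everyone without a Week 6 value. It does not say so: no time point or complete-case rule is given, and this is only the ordinary reading of an ANCOVA without imputation. A reader might also infer that the zibotentan effect will be understated. That needs both a true effect and dropout linked to diuretic use, and the documents establish neither.

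**Conclusion.** The point holds as a gap between what SAP 4.2.3.5 claims and what it specifies. Key objectives 5 and 6 have no described missing-data check, and the plan's own sister sections show what one would look like. If run on observed Week 6 values, the ANCOVA would differ from the MMRM in both method and participants.

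The shrinkage is conditional: about 5% to 13% in the main simulation, up to 25% under the harsher hazards, and none with random dropout. All of these rest on assumed dropout, effect and link to diuretic use. The number affected is probably small, and the primary MMRM is not affected. The change is worth making because it is nearly free and the endpoint is a key one; it does not put the main result in doubt.

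**What to change.** In SAP 4.2.3.5, specify an ANCOVA on the Week 6 cumulative change after multiple imputation under MAR by treatment group, using the observed cumulative values at earlier weeks, with 1000 imputations and seed 4567 to match 4.2.2.5 and 4.2.5.5. Name the covariates. In 4.2.3.3, state that weeks after study withdrawal are missing and are not counted as zero use.

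The cost is two or three sentences, and the same approach is already specified for two other endpoints. One small downside is that many participants may have zero change, so the imputation model must cope with a spike at zero.

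If the sponsor holds that no value can be missing, the alternative is to delete the reference to missing data from the opening line and say why.

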4.2.3.6 Supplementary Analyses of the key objective

Not applicable.

4.2.3.7 Subgroup Analyses

The primary analysis of this endpoint will be performed for the subgroups defined in section 3.3.1.7 if appropriate.

4.2.4 Key Objective 7 and 8, Composite endpoint of water and loop-diuretic

4.2.4.1 Definition

Estimand is defined in section 4.2.

4.2.4.2 Derivations

The endpoint will be assessed throughout the time period, looking at each observation compared to baseline. For loop-diuretic derivation see section 3.3.1.5. The composite variable will be yes if any event has occurred on or prior to analyses date.

4.2.4.3 Handling of Dropouts and Missing Data

No imputation of missing will be performed.

4.2.4.4 Primary Analysis of key objective

Exact 90% (two-sided) CIs for proportions of participants with the composite of fluid retention in treatment groups will be calculated using the Clopper-Pearson method. The exact unconditional 90% (two-sided) CIs for pairwise difference in proportions between 2 treatment groups compared, as specified in objectives, will be computed based on score statistic (Chan and Zhang, 1999). CCI will also be presented.

4.2.4.5 Sensitivity Analyses of the key objective

Following analysis for evaluating impact of missing data will be done:

- A conservative imputation approach will be conducted and missing data will be imputed for each component separately except for component of fluid retention AEs. The placebo group will have missing data imputed as “No event”. For the zibotentan/dapagliflozin and zibotentan monotherapy treatment groups the missing data will be imputed based on the overall probability for “Event” at a given visit in the combined zibotentan/dapagliflozin and zibotentan monotherapy treatment groups. This probability will be estimated using the observed probability. For component of fluid retention AEs, no imputation will be done. The analyses method will follow section 4.2.4.4.

4.2.4.6 Supplementary Analyses of the key objective

Not applicable.

4.2.4.7 Subgroup Analyses

The primary analysis of this endpoint will be performed for the subgroups defined in section 3.3.1.7 if appropriate.

4.2.5 Key Objective 9 and 10, Change from baseline in Systolic and diastolic blood pressure

4.2.5.1 Definition

Estimand is defined in section 4.2. Supine blood pressure will be analysed.

4.2.5.2 Derivations

Not applicable.

4.2.5.3 Handling of Dropouts and Missing Data

Missing data is assumed to be MAR and no imputation will be done.

4.2.5.4 Primary Analysis of key objective

Will be analysed using MMRM methodology. The analytic model will include the CCI [REDACTED] of CCI [REDACTED], and CCI [REDACTED], and CCI [REDACTED] CCI [REDACTED]. An CCI [REDACTED] will be used for the CCI [REDACTED].

4.2.5.5 Sensitivity Analyses of the key objective

Following analysis for evaluating impact of analyses method and missing data will be done:

- To analyse the method choice of MMRM the analyses will be performed using ANCOVA after missing data has been imputed under MAR assumption using multiple imputation. A total of 1000 imputations will be performed using a seed of 4567.

4.2.5.6 Supplementary Analyses of the key objective

Not applicable.

4.2.5.7 Subgroup Analyses

The primary analysis of this endpoint will be performed for the subgroups defined in section 3.3.1.7 if appropriate.

4.2.6 Exploratory Objective 1, PK-analyses

4.2.6.1 Definition

PKS analysis set will be used. Estimand is defined in section 4.2.

4.2.6.2 Derivations

Not applicable.

4.2.6.3 Handling of Dropouts and Missing Data

Missing data is assumed to be MAR and no imputation will be done.

4.2.6.4 Primary Analysis of exploratory objective

The data will be descriptively summarised by treatment group, visit, and time-point. Geometric mean and CV will be presented in addition to arithmetic mean and SD. PK assessments that should only be collected once according to schedule of activities in CSP will be summarised using the assessment closest to target date even if outside of visit windowing.

Additional PK analyses may be conducted as appropriate but will be reported outside the CSR.

4.2.6.5 Additional Analyses of the exploratory objective

Not applicable.

4.2.6.6 Subgroup Analyses

Not applicable. Certain analyses will be divided into Japanese vs non-Japanese based on the collection specified in CSP.

4.2.7 Exploratory Objective 2, Change from baseline in CCI and CCI

This exploratory endpoint might not be collected for all subjects and is collected at screening and Visit 6, see CSP for details on data collection.

4.2.7.1 Definition

Estimand is defined in section 4.2.

4.2.7.2 Derivations

Not applicable.

4.2.7.3 Handling of Dropouts and Missing Data

Missing data is assumed to be MAR and no imputation will be done.

4.2.7.4 Primary Analysis of exploratory objective

The analysis is performed using ANCOVA for both absolute and percentage change from baseline. The data will be descriptively summarised by treatment group and presenting absolute and percentage change from baseline.

4.2.7.5 Additional Analyses of the exploratory objective

Not applicable.

4.2.7.6 Subgroup Analyses

Not applicable.

4.2.8 Exploratory Objective 3, Change from baseline in AST, ALT and MELD- score

4.2.8.1 Definition

Estimand is defined in section 4.2.

4.2.8.2 Derivations

Data for AST, ALT taken from safety data. MELD score is derived as defined in section 3.3.1.6.

4.2.8.3 Handling of Dropouts and Missing Data

Missing data is assumed to be MAR and no imputation will be done.

4.2.8.4 Primary Analysis of Exploratory objective

The analysis is performed using MMRM, similar to key objective, for both absolute and percentage change from baseline for AST and ALT and for absolute change for MELD score. The data will be descriptively summarised by treatment group and visit. For AST and ALT absolute and percentage change from baseline will be presented. For MELD score absolute change from baseline will be presented.

4.2.8.5 Additional Analyses of the Exploratory objective

Not applicable.

4.2.8.6 Subgroup Analyses

Not applicable.

4.2.9 Exploratory Objective 4, Change from baseline in Blood biomarkers

4.2.9.1 Definition

The variables to be analysed are: Plasma/serum CCl

Estimand is defined in section 4.2.

4.2.9.2 Derivations

Not applicable.

4.2.9.3 Handling of Dropouts and Missing Data

No imputation will be done.

4.2.9.4 Primary Analysis of Exploratory objective

The analysis is performed using MMRM, similar to key objectives, for absolute change from baseline. Data will be summarised descriptively by treatment group and visit.

4.2.9.5 Additional Analyses of the Exploratory objective

Not applicable.

4.2.9.6 Subgroup Analyses

Not applicable.

